4.2. NON-INCLUSION CRITERIA

1. Any previous treatment with a PARP inhibitor, including Olaparib,
2. Patients unable to swallow orally administered medication and patients with gastrointestinal disorders likely to interfere with absorption of the study medication,
3. Immunocompromised patients, e.g., patients who are known to be serologically positive for human immunodeficiency virus (HIV) and are receiving antiviral therapy,
4. Patients with known active hepatic disease (i.e., Hepatitis B or C) due to risk of transmitting the infection through blood or other body fluids,
5. Patients considered a poor medical risk due to a serious, uncontrolled medical disorder, non-malignant systemic disease or active, uncontrolled infection. Examples include, but are not limited to, uncontrolled ventricular arrhythmia, recent (within 3 months) myocardial infarction, unstable spinal cord compression (untreated and unstable for at least 28 days prior to study entry), superior vena cava syndrome, extensive bilateral lung disease on HRCT scan or any psychiatric disorder that prohibits obtaining informed consent,
6. Patients with uncontrolled seizures,
7. Men or women of childbearing potential who are not using an effective method of contraception as previously describes; women who are pregnant or breast feeding,

8. Prior or concurrent malignant disease diagnosed or treated in the last 2 years, except for adequately treated in situ carcinoma of the cervix, basal or squamous skin cell carcinoma, or in situ transitional bladder cell carcinoma,
9. Patients receiving any systemic chemotherapy, radiotherapy (except for palliative reasons), within 2 weeks from the last dose prior to study treatment (or a longer period depending on the defined characteristics of the agents used),
10. Concomitant use of known strong CYP3A4 inhibitors (such as ketoconazole, itraconazole, boosted protease inhibitors, indinavir, saquinavir, telithromycin, clarithromycin, nelfinavir, boceprevir and telaprevir), moderate CYP3A4 inhibitors (such as ciprofloxacin, erythromycin, diltiazem, fluconazole, verapamil), strong CYP3A4 inducers (such as phenobarbital, enzalutamide, phenytoin, rifampicin, rifabutin, rifapentine, carbamazepine, nevirapine and St John's Wort) and moderate CYP3A4 inducers (such as bosentan, efavirenz, modafinil),
11. Resting ECG with QTc > 470msec on 2 or more time points within a 24 hour period or family history of long QT syndrome,
12. Blood transfusions within 14 days prior to study start,
13. Patients with myelodysplastic syndrome/acute myeloid leukaemia,
14. Major surgery within 14 days of starting study treatment
15. Participation to a study involving a medical or therapeutic intervention in the last 30 days,
16. Patient unable to follow and comply with the study procedures because of any geographical, familial, social or psychological reasons,
17. Previous enrolment in the present study,
18. Patients with a known hypersensitivity to olaparib or any of the excipients of the product,
19. Patients who not have recovered from any effects of any major surgery,
20. Individuals deprived of liberty or placed under legal guardianship.
21. Patients who have tumor in contact with, invading or encasing for more than 50% any major blood vessels and/or patients requiring vascular reconstruction.

5. STUDY PLAN

5.1. DURATION OF STUDY (WHOLE POPULATION)

The total duration of the study will be approximately 68 months, including about 56 months of active enrollment.

Planned start date (first patient on study): October 2016.

Within each cohort (dose escalation and expansion cohort), the planned cohort termination (clinical cutoff) corresponds to the date when each patient has been followed-up for 12 months or is deceased.

- End of study occurs when all of the following criteria have been satisfied:
 - The trial is closed to recruitment
 - AND
 - All participants have disease progression or are no longer on study medication
 - AND
 - The last included participant has been followed for 12 months, or if deceased each participant has been followed up for 12 months or is deceased

5.2. DEFINITIONS OF DURATION OF STUDY AND TREATMENT (PER PATIENT)

Patients will receive study treatment until the end of the radiotherapy and as long as it is considered to be in their best interest. After the end of radiotherapy, Olaparib could be continued until progression (locoregional and/or metastatic progression) at the investigator's discretion and sponsor should be informed. Patients will be evaluated at scheduled visits in up to three study periods:

- **Pre-treatment (PRE TT):** from signature of informed consent to the first administration of study drugs.
- **Treatment (TT):** from the first administration of study drugs to treatment discontinuation defined as :
 - 30 days after the last dose of treatment of Olaparib and/or
 - 6 weeks after the last dose of radiotherapy.

Note: if surgery performed, patient will be followed up at D30, D60 and D90 post surgery. Then the patient will be followed up according to FUP below.

- **Follow-up (FUP):** after treatment discontinuation, patients will be followed up four weeks later for

toxicities, and beyond if grade 3 or 4 toxicity, until resolution.

After documented progression (locoregional and/or metastatic progression) or start of a new antitumor therapy, patients will be **followed every 3 months until**:

1. Death, or
2. The end of the follow-up period, whichever occurs first.

Patients will be considered to be **on-study** from the signature of the informed consent to the end of follow-up period.

Patients will be considered to be **on-treatment** for the duration of their treatment until 30 days after the last dose of Olaparib and/or 6 weeks after the last dose of radiotherapy, except if the patient starts a new antitumor therapy before this period.

Patients may withdraw their consent at any time; no further study activities will be conducted on them.

Treatment discontinuation occurs when an enrolled patient ceases to receive the study medication or starts a new antitumor therapy, regardless of the circumstances, and is defined as 30 days after the last dose of Olaparib and/or 6 weeks after the last dose of radiotherapy, unless the patient starts a new antitumor therapy, in which case the date of administration of this new antitumor therapy will be considered the date of treatment discontinuation. The primary reason for any discontinuation will be recorded on the patient's Case Report Form (CRF). If a patient discontinues treatment, every effort should be made to complete the scheduled assessments. Administration of the study treatment should be discontinued if this is considered to be in the best interest of the patient. More specifically, treatment will be discontinued due to any of the following reasons:

- Disease progression (locoregional and/or metastatic progression),
- Unacceptable toxicity,
- Intercurrent illness of sufficient magnitude to preclude safety continuation of the study,
- Patient refusal and/or non compliance with study requirements,
- Protocol deviation with an effect on the risk/benefit ratio of the clinical trial

Patients still experiencing a non-progression rate after the end of the radiotherapy will then be able to continue Olaparib at the discretion of the investigator and after sponsor approval.

Study discontinuation occurs when an enrolled patient ceases to participate in the study, regardless of the reason (as detailed under "Follow-up" in Section 5.8). Patients have the right to withdraw consent at any time; if this is the case, no further follow-up should be performed.

The date and reason for study discontinuation will be clearly documented on the patient's CRF.

5.3.PROTOCOL DEVIATION

A protocol deviation is defined as any departure from what is described in the protocol of a clinical trial approved by an Independent Ethics Committee/Institutional Review Board (IEC/IRB) and Competent Authorities. Therefore, this applies to deviations related to patient inclusion and clinical procedures (e.g., assessments to be conducted or parameters to be determined), and also to other procedures described in the protocol that concern the Good Clinical Practice (GCP) guidelines or ethical issues (e.g., issues related to obtaining the patients' Informed Consent, data reporting, the responsibilities of the investigator, etc.).

Deviations with no effects on the risk/benefit ratio of the clinical trial (such as minimal delays in assessments or visits) will be distinguished from those that might have an effect on this risk/benefit ratio, such as:

- Deviations that might affect the clinical trial objectives, such as those involving the inclusion/exclusion criteria (which could mean that the patient is not eligible for the trial) and those having an effect on patient evaluability.
- Deviations that might affect the patient's well-being and/or safety, such as an incorrect dosing of the investigational medicinal product (plitidepsin) due to not following dose adjustment specifications or an incorrect preparation of the medication.
- Deviations related to the following of GCP guidelines as described in the protocol and regulations in force, such as deviations when obtaining the Informed Consent or not following the terms established for reporting serious adverse events, etc.

The investigators may suggest to the Sponsor the authorization of certain protocol deviations, especially

if they are related to the inclusion/exclusion criteria or if they may have an effect on the evaluability of the patients. As a general rule, NO deviations that may have an effect on the risk/benefit ratio of the clinical trial will be authorized. Protocol deviations considered particularly relevant, which are related to ethical issues, fulfillment of GCP guidelines and trial procedures, will be notified to the pertinent IEC/IRB and, if pertinent, to the relevant authorities as established by local regulations.

5.4.SCREENING EVALUATION

During the pre-treatment period, and once the patient has signed the Informed Consent Form, the Investigator will confirm the patient's eligibility for the study by conducting the assessments detailed in Table below.

Table. Screening assessments.

	ASSESSMENT	TIME
1. History and clinical examination	♦ Signed by the patient/legal representative Informed Consent Form	Prior to any specific study procedures
	♦ Medical history and baseline condition ♦ Complete physical examination ♦ Performance status (ECOG PS; see Appendix 1) ♦ Assessment of baseline signs and symptoms ♦ Concomitant treatments	Within two weeks prior to Day 1 (+1 week tolerance)
	♦ Vital signs: heart rate, blood pressure, body temperature, weight and height	Within 7 days prior to Day 1 (+1 day tolerance)
	♦ Demographic data ♦ Primary diagnostic and prior treatment/s data: – Date of diagnosis of the primary disease – Prior treatments (surgery, radiotherapy, chemotherapy, immunotherapy), specifying the date of best response and the time to progression	Within four weeks prior to Day 1 (+2 weeks tolerance)
2. Pathology	♦ Central review to confirm soft-tissue sarcoma diagnosis, except in case of diagnosis confirmed by RRePS Network	Material sent within 7 days next to signed informed consent
3. Laboratory tests	♦ Hematology: differential WBC, ANC, haemoglobin, platelets, RBC, MCV, MCHC, MCH ♦ Biochemistry: Serum electrolytes (Na ⁺ , K ⁺ , Mg ⁺⁺ and Ca ⁺⁺), liver function tests (AST, ALT, total bilirubin, GGT and AP), LDH, creatinine, fasting glucose, total proteins, urea, albumin ♦ Coagulation: TP, INR, aPTT ♦ Urinary: dipstick	Within 7 days prior to Day 1 (+3 days tolerance). In the event that the patient's condition is deteriorating, laboratory evaluations should be repeated within 48 hours prior to initiation of the treatment
		Within 7 days prior to Day 1 (+3 days tolerance)
4. Creatinine clearance	♦ Calculated according local institution (see Appendix 2)	Within 7 days prior to Day 1 (+3 days tolerance)
5. Pregnancy test, if applicable	Measurement of serum human chorionic gonadotropin (HCG)	Within 28 days prior to Day 1 (+1 day tolerance).
6. ECG	♦ QTc measurement: twelve-lead ECGs will be obtained after the patient has been rested in a supine position for at least 5 minutes. ECGs will be recorded at 25 mm/sec.	Within 7 days prior to Day 1 (+3 days tolerance) and repeated within 24 hours if > 470msec
7. Tumor assessment	♦ MRI for upper/lower limb or trunk wall sarcoma of all measurable sites, as per RECIST (Appendix 3) ♦ CT Scan only for patients with metastatic disease	Within four weeks prior to Day 1 (+1 week tolerance)
8. Other tests	♦ Intercurrent events, concomitant diseases and treatments.	Within two weeks prior to Day 1.

ALT, alanine aminotransferase; ANC, absolute neutrophil count; AP, alkaline phosphatase; aPTT, activated partial thromboplastin time; AST, aspartate aminotransferase; ECG, electrocardiogram; ECOG PS, Eastern Cooperative Oncology Group Performance Status; INR, International Normalized Ratio; LDH, lactate dehydrogenase; MCH, mean cell haemoglobin; MCHC, mean cell haemoglobin concentration; MCV, mean cell volume; MRI, magnetic resonance imaging; RBC, red blood cell; RECIST v1.1, Response Evaluation Criteria In Solid Tumors; TP, prothrombin Rate; WBC,

	ASSESSMENT	TIME
--	------------	------

white blood cells.

5.5.EVALUATIONS DURING TREATMENT

The following assessments will be done while the patient is on treatment.

Table. Evaluations during treatment

	ASSESSMENT	TIME
1. Clinical examination	
 Complete physical examination Performance status (ECOG PS; see Appendix 1) Vital signs: heart rate, blood pressure, body temperature and weight 	
Repeat up to 48 hours before Day 1
 
Repeat on Day 1 of each subsequent week during radiotherapy: on Day 8, 15, 22, 29, 36, 43 and 50.
 
Repeat on week 10, 12, 14 and 24 thereafter in case of Olaparib discontinuation after the end of radiotherapy
 
Repeat on Day 1 of each subsequent month in case of Olaparib continuation after the end of radiotherapy.

	
 Assessment of baseline signs and symptoms 	Throughout the treatment period
	
 Concomitant diseases and treatments 	Throughout the treatment period
	
 Functional assessment MSTs 	Completed by the radiotherapist at baseline and at the end of radiotherapy treatment
2. Laboratory tests*	
 Hematology: differential WBC, ANC, haemoglobin, platelets, RBC, MCV, MCHC, MCH Biochemistry: Serum electrolytes (Na⁺, K⁺, Mg⁺⁺ and Ca⁺⁺), liver function tests (AST, ALT, total bilirubin, GGT and AP), LDH, creatinine, fasting glucose, total proteins, urea, albumin Coagulation: TP, INR, aPTT, if clinically indicated Urinary: dipstick if clinically indicated 	
Repeat up to 48 hours before Day 1
 
Repeat every two weeks, on Days 15, 29 and 43
 
Repeat on week 10, 12, 14 and 24 thereafter in case of Olaparib discontinuation after the end of radiotherapy
 
Repeat on Day 1 of each subsequent month in case of Olaparib continuation after the end of radiotherapy.
 
 If clinically indicated
3. Creatinine clearance	
 Calculated according local institution (see Appendix 2) 	
Repeat up to 48 hours before Day 1
 
Repeat every two weeks, on Days 15, 29 and 43
 
Repeat on week 10, 12, 14 and 24 thereafter in case of Olaparib discontinuation after the end of radiotherapy
 
Repeat on Day 1 of each subsequent month in case of Olaparib continuation after the end of radiotherapy.

4. Pregnancy test, if applicable	
 Measurement of serum human chorionic gonadotropin (HCG) 	
On day 1 prior to the start of study treatment.
 
In the event of a suspected pregnancy during the study, the test should be repeated.

5. ECG	
 QTc measurement: twelve-lead ECGs will be obtained after the patient has been rested in a supine position for at least 5 minutes. ECGs will be recorded at 25 mm/sec. 	
At week 10
 
 If clinically indicated
6. Tumor assessment	
 MRI of all measurable sites, as per RECIST (see Appendix 3) CT Scan only for patients with metastatic disease 	
Tumor assessment must be repeated
 
 MRI: every twelve weeks (±7 days) and at least four weeks after first documentation of objective response even if there are treatment delays: on weeks 12 and 24. CT Scan: every 8 weeks.
7. PK study	
 Blood samples 	See section 17.1.1
8. Optional biopsy	
 Predictive markers of treatment outcome from tumor samples 	See section 17.2.1
9. AEs	As per NCI-CTCAE, version 4.	Throughout the treatment period

*For all laboratory tests a window of 72 hours will be allowed.

ALT, alanine aminotransferase; ANC, absolute neutrophil count; AP, alkaline phosphatase; aPTT, activated partial thromboplastin time;

	ASSESSMENT	TIME
AST, aspartate aminotransferase; ECG, electrocardiogram; ECOG PS, Eastern Cooperative Oncology Group Performance Status; INR, International Normalized Ratio; LDH, lactate dehydrogenase; MCH, mean cell haemoglobin; MCHC, mean cell haemoglobin concentration; MCV, mean cell volume; MRI, magnetic resonance imaging; RBC, red blood cell; RECIST v1.1, Response Evaluation Criteria In Solid Tumors; TP, prothrombin Rate; WBC, white blood cells.		

5.6.EVALUATION AT END OF TREATMENT

The end-of-treatment visit will be scheduled:

- 30 days (4 weeks) after the last Olaparib administration (a window of ± 1 week is allowed) and/or
- 6 weeks after the last dose of radiotherapy.

Regardless of the reason for discontinuation, the complete workup has to be done at the end-of-treatment visit. This will include the following assessments:

- Assessment of signs and symptoms.
- Complete physical examination.
- ECOG performance status.
- Vital signs [heart rate, blood pressure, and temperature].
- Hematology.
- Biochemistry.
- Calculated CrCl.
- Electrocardiogram (QTc measurement: twelve-lead ECGs will be obtained after the patient has been rested in a supine position for at least 5 minutes. ECGs will be recorded at 25 mm/sec.)
- Clinical and radiological tumor assessment (MRI and CT Scan if metastatic disease at inclusion) (except for patients with confirmed PD at discontinuation or who had started a new treatment).
- Intercurrent events and concomitant disease and treatments.
- Safety assessment (AEs).

Adverse events must be reported for 30 days after the last dose of Olaparib and/or 6 weeks after the last dose of radiotherapy administration or until the start of a new antitumor therapy, whichever occurs first. All SAEs occurring within 30 days after the last dose of Olaparib and/or 6 weeks after the last dose of radiotherapy or until the start of a new antitumor therapy, whichever occurs first, will be reported. Beyond this period of time, only those SAEs suspected to be treatment-related (Olaparib/radiotherapy) or research-related (diagnostic procedures, examinations carried out during the research...) will be reported (see Section 11).

In case of surgery, post surgery complications must be reported during 12 months after the surgery unless start of a new anti-tumor therapy.

5.7.FOLLOW-UP AFTER END-OF-TREATMENT VISIT

- Each patient will be followed-up for 12 months after inclusion.
- The date and reason of the study discontinuation will be recorded on the patient's CRF (see Section 5.2).
- After treatment discontinuation, patients will be followed every 3 months until death or until the end of the follow-up period, whichever occurs first.
- Patients who withdraw consent will not be followed with any study procedures.

All AEs (including SAEs) suspected to be treatment-related (Olaparib and/or radiotherapy) or research-related will be followed-up until the events or their sequelae resolve or stabilize at a level acceptable to the Investigator and the Sponsor.

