The toxicology studies indicate that the target organ of toxicity is the bone marrow.

Further information can be found in the current version of the olaparib IB.

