3. STUDY DESIGN

3.1.OVERALL STUDY DESIGN

This is a multicenter, prospective phase Ib trial based on a dose escalation study design assessing four dose levels of Olaparib given with concomitant radiotherapy, followed by an expansion cohort once the recommended phase II dose (RP2D) has been established.

3.2.RATIONALE FOR STUDY DESIGN AND DOSES

Few clinical data about combination of Olaparib and radiotherapy are available and more or less about Olaparib and STS radiotherapy. Therefore, a phase 1 dose escalation trial has been designed in order to determine the MTD and the safety of the combination. An expansion cohort should allow to appreciate anti-tumor activity of the combination.

Study population was defined as patients with locally advanced/unresectable STS (with or without metastases) because their outcome with radiotherapy alone is very poor.

The choice of olaparib doses was based on preclinical data showing that low doses are sufficient with radiotherapy.

3.3.DEFINITIONS

Dose-limiting toxicity (DLT)

A DLT is defined as an adverse event (AE) or laboratory abnormality that fulfills all the criteria below:

- Occurs during the period of observation of DLTs defined as the period between the first day of treatment administration and up to 6 weeks after the end of radiotherapy.
- Is considered to be at least possibly related to the treatment strategy (radiotherapy or Olaparib).
- Is unrelated to disease, disease progression, inter-current illness, or concomitant medications.
- Meets one of the criteria below, graded as outlined or according to NCI CTCAEv4.0:
 - Any grade ≥ 3 musculoskeletal or cutaneous toxicity within the field of radiation:
 - Occurring at a radiotherapy dose $< 30\text{Gy}$
 - Occuring at a radiotherapy dose $\geq 30\text{Gy}$ and without regress to a grade ≤ 2 in a time limit of 4 weeks
 - Any non-hematological toxicity \geq grade 3 (except for nausea, vomiting, fatigue, alopecia and fever)
 - Laboratory abnormality \geq grade 3 lasting > 5 days (except for lymphopenia, hyperglycaemia and changes in serum electrolytes/enzymes without clinical impact)

- Febrile neutropenia (absolute neutrophil count [ANC] < 1.0 x10⁹/L and fever ≥ 38.5°C) and/or documented infection with ANC < 1.0 x 10⁹/L
- Grade 4 neutropenia (absolute neutrophil count < 500) lasting ≥ 7 days
- Grade 4 thrombocytopenia or bleeding requiring a platelet transfusion
- Any other toxicity grade ≥ 4

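### Two DLT criteria depend on how long a laboratory abnormality lasts, but section 5.5 and the schedule table give different blood sampling inside the DLT window, and under 5.5 patients who stay on olaparib are sampled least

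*Protocol*

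**What the plan says.** Protocol 3.3 defines two DLT criteria by duration. One is a laboratory abnormality at or above "grade 3 lasting > 5 days (except for lymphopenia, hyperglycaemia" and certain electrolyte or enzyme changes). The other is "Grade 4 neutropenia (absolute neutrophil count < 500) lasting ≥ 7 days". Other haematological criteria have no duration condition, for example "Grade 4 thrombocytopenia or bleeding requiring a platelet transfusion".

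On sampling, Protocol 5.5 gives bloods shortly before Day 1 and then "Repeat every two weeks, on Days 15, 29 and 43". After radiotherapy it splits patients. Those who stop olaparib have bloods at weeks 10, 12, 14 and 24. For the others it says "Repeat on Day 1 of each subsequent month in case of Olaparib continuation after the end of radiotherapy".

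The schedule of assessments in the synopsis differs. Its haematology and biochemistry rows add Day 50 and show weeks 10, 12 and 14 (Days 64, 78 and 92) for all patients. Its footnote starts the monthly visits for continuing patients at week 16.

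The DLT window is 13.5 weeks (3.4.1). Section 1.2 says: "The toxicology studies indicate that the target organ of toxicity is the bone marrow".

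**The concern.** A criterion that turns on 5 or 7 days needs samples close enough together to time an episode. With draws 14 or more days apart, an episode can begin and end unseen, or appear once and never be timed.

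The two sampling descriptions also disagree within the DLT window. A site that follows 5.5 as written takes no Day 50 draw and samples a patient still on olaparib less often than one who has stopped. DLT ascertainment would then differ with exposure, in the wrong direction.

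In the TITE-CRM, a patient with no recorded DLT contributes follow-up weighted by the share of the window completed (3.4.2). A missed or untimed episode therefore lowers the estimated DLT probability against the 33% target. It never raises it.

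**Working it through.** **Inputs.** The draw days come from 5.5 and the schedule table. Radiotherapy ends at about D52 (synopsis, route of administration). The DLT window is 1 + 6.5 + 6 = 13.5 weeks, which agrees with 3.4.1, and ends at D52 + 42 = D94. The plan's two-week interval is confirmed: 29 − 15 = 43 − 29 = 14 days.

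**Gaps between draws.**
- 5.5, olaparib stopped (D1, 15, 29, 43, 64, 78, 92): 14, 14, 14, 21, 14, 14. Without Day 50, the gap from D43 to D64 is 21 days.
- 5.5, olaparib continued: 14, 14, 14, then monthly. The start of the monthly cycle is not stated, so I assumed a first draw at D57 (and a second at D85), at D71 or at D82.
- Schedule table (adds D50): 14, 14, 14, 7, 14, 14, 14.

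**Chance that an episode of L days meets no scheduled draw.** Assume onset is uniform from D2, the episode lies wholly within the window, draws fall on their nominal days and there are no unscheduled draws. There are 94 − L possible start days. The starts that meet no draw number the sum over gaps of (gap − L), where positive, plus (95 − last draw day − L), where positive. With steady 14-day sampling this reduces to 1 − L/14.

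Examples for L = 6:
- 5.5 stopped: (5×8 + 15)/88 = 55/88 = 62.5%.
- 5.5 continued, first draw D71: (3×8 + 22 + 18)/88 = 64/88 = 73%.
- Schedule table: (6×8 + 1)/88 = 49/88 = 56%.

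| Schedule | 6 days | 7 days | 10 days | 13 days |
|---|---|---|---|---|
| Steady 14-day draws | 57% | 50% | 29% | 7% |
| 5.5, olaparib stopped | 62.5% | 56% | 37% | 16% |
| 5.5, olaparib continued | 66–73% | 60–68% | 40–52% | 23–36% |
| Schedule table | 56% | 48% | 29% | 7% |

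**Chance of two scheduled draws.** Under 5.5 it is zero for every length from 6 to 13 days. In the schedule table only D43 and D50 are close enough. An episode must cover 8 calendar days to include both, so the chance is (L − 7)/(94 − L): 0 at 6 and 7 days, 1/86 = 1% at 8, 3/84 = 4% at 10 and 6/81 = 7% at 13.

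**End-of-treatment bloods (5.6).** These fall 30 days after the last olaparib dose and/or 6 weeks after radiotherapy. If olaparib stops at D52, the first option is D82, which splits the gap from D78 to D92 into 4 and 10 days. The no-draw chance at 6 and 7 days becomes 51/88 = 58% and 45/87 = 52% under 5.5, and 45/88 = 51% and 38/87 = 44% under the table. D78 and D82 together span 5 calendar days, so that pair alone cannot show more than 5. The second option, D94, changes none of these figures.

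**Laboratory window.** Section 5.5 allows 72 hours and gives no sign. Read as ±3 days, a 14-day gap becomes anything from 8 to 20 days.

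**The case against.** The strongest reply is that the trial does not rely on scheduled draws alone. Neutropenia of grade 3 or worse requires interruption and close follow-up (7.1.6.4), and restart after neutropenia or severe anaemia depends on a recovered count (7.1.6.3, 7.1.6.4), so a repeat sample must be taken. Any grade 4 laboratory result is a serious adverse event (11.2.2), to be followed to resolution. Febrile neutropenia, grade 4 thrombocytopenia, other grade 4 toxicity and a toxicity-related olaparib interruption of 14 days or more are DLTs by other routes. Investigators, with the sponsor, may also declare other significant drug-related toxicity a DLT.

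Much of this stands. A reader might infer that haematological DLTs in general hinge on duration; only two criteria do. A reader might also infer that a 6 to 13 day episode can never be shown to be a DLT. The documents do not support that either: the D43/D50 pair, the end-of-treatment bloods, the laboratory window or a repeat count could show it.

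What the reply does not supply is timing. No interval is set for close follow-up, for serious adverse events or for following related events to resolution (5.7). Weekly counts begin only after an interruption of two weeks or more (7.1.6.6), too late for these episodes. Under 11.8.2, deterioration in a protocol-mandated laboratory value is an adverse event only if it meets a seriousness criterion or causes discontinuation, so an isolated grade 3 value may not be recorded as one. None of these routes finds an episode that no draw met.

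The schedule table does keep weeks 10, 12 and 14 for continuing patients, so the sparse monthly sampling is one of two conflicting readings. That is the reason to reconcile them.

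**Conclusion.** The point holds in limited form. Sections 3.3 and 5.5 and the schedule table do not fit together. Under 5.5 there is a 21-day gap for patients who stop olaparib, and those who continue are sampled least within the DLT window. Roughly half or more of 6 to 7 day episodes meet no scheduled draw: 48% to 73% across the readings, or 44% to 58% for patients who stop at D52 if an end-of-treatment draw near D82 is counted. The duration of a 6 to 13 day episode usually cannot be established from scheduled draws alone.

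These percentages are conditional on an episode occurring and rest on uniform onset and nominal draw days with no unscheduled samples. It is tempting to conclude that the MTD will be set too high by a material amount. The documents do not support that: they give no frequency for such episodes, so only the direction, toward tolerability, can be stated.

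**What to change.** Reconcile 5.5 with the schedule table (Day 50, weeks 10, 12 and 14, and the start of monthly visits) so that one sampling schedule applies to all patients throughout the DLT window, whether or not olaparib continues. Which schedule that should be is for the sponsor.

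In the SAP, keep the DLT definition and add a sensitivity analysis of the end-of-trial posterior planned in Protocol 10.3. Count as a DLT any otherwise qualifying laboratory value of grade 3 or worse (grade 4 for neutropenia) with no later sample documenting recovery within the stated duration limit. At present SAP 3.2.1.1 only checks that the DLT fields are completed, while Tables 9.4 and 9.6 report by the duration criteria. The analysis can be run on bloods already collected.

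This should not become the primary counting rule. It would make every unrepeated qualifying value a DLT, change the rule that drives dose assignment, and still not recover episodes that no sample met.

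The cost is a wording change, a little more analysis work and possibly a few draws that the table already lists.
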